2.3 Prior Investigations and Market Experience

The Tango Belt was previously marketed as a personal safety product and has been used in senior care facilities (including Skilled Nursing Facilities, Assisted Living Facilities, and Continuing Care Retirement Communities) and in-home environments. Following extensive laboratory testing, a pre-production version of the Tango Belt was initially introduced into multiple senior care facilities in a series of pilots beginning in 2017. The production version was then introduced into senior care facilities and in-home environments beginning in 2019. To date, the Tango Belt has been worn for over 80,000 hours of cumulative wear by over 100 older adults within home and senior care settings since its introduction as a personal safety product.

Real-world evidence from this previous use provides insight into the belt's potential to mitigate the injury risk associated with hip-impacting falls. Published case series demonstrated that the belt appropriately detected falls in-progress and could discriminate between non-serious and serious hip-impacting falls. In addition, the belt successfully delivered automated fall notifications to designated caregivers when a fall occurred. *V Most notably, unpublished data of real-world evidence demonstrates the Tango Belt was able to reduce the overall rate of falls with major injury by 60% over 6 months in a pilot conducted in a large skilled nursing facility. Further, the ability of the airbag technology to mitigate fall-related injury in a serious hip-impacting fall without causing harm to the wearer has been demonstrated. Lastly, the belt has shown strong adherence to wear, with a previously published case series demonstrating that it could

be worn comfortably for prolonged durations with wear times exceeding 12 hours and with belt removal needed only for charging or for bathing. xvi

These initial case series demonstrate the utility of the Tango Belt in higher-fall-risk patients and warrant further investigation in a controlled study to specifically establish the safety and effectiveness of the Tango Belt for the mitigation of falls with major hiprelated injury in an at-risk, older adult population.

2.4 Demonstration of the Safety and Effectiveness of study product

Laboratory performance testing of the serious hip-impacting fall-in-progress detection algorithm was conducted using APT's staged true-fall library and demonstrated sensitivity of 82%. This testing includes inertial data sensor recording, prototype sensor and airbag-disabled belt assemblies, and pre-production sensor and airbag-disables belt assemblies. Further, with respect to specificity, there were 10 false positives (i.e., false alarms) over 66,000 wear-hours. Laboratory testing includes extensive design verification testing to confirm safety and functionality of the hardware and software, including impact attenuation on crash test dummies, environment conditioning, out-of-position deployment, FCC certification, electromagnetic emissions and immunity, belt and companion app usability, etc. In conjunction with the real-world evidence noted above, testing performed to date has demonstrated that the Tango Belt is safe and performs as intended.

2.5 Potential Known Risks and Benefits

Risks to subjects in this study include, but are not limited to, the following: use error or ineffective intervention leading to impact-related injury, adverse tissue reactions and interference with other electrical equipment/devices.

Presently, there are no known adverse events associated with the Tango Belt itself that have arisen throughout the pre-clinical testing and real-world usage.

Potential benefits of the Tango Belt include mitigating major hip injuries due to falls and reducing emergency department visits and hospitalizations due to falls, thereby enabling safer mobility in older adults at risk of falls and fall injuries.

3. Purpose/Intended Use

Purpose:

The current comparative clinical study is intended to establish the safety and effectiveness of the Tango Belt as an adjunctive intervention to the standard-of-care (SOC) to mitigate major hip injuries due to falls in an older adult population at-risk for fall injury.

Intended Use:

The Tango Belt is intended to be worn around the waist by geriatric individuals (65+ years of age) at risk for fall injury in order to mitigate major hip injuries related to falls. The Tango Belt uses built-in sensors and algorithms to detect falls and impacts. The device can send an alert to the designated caregiver/healthcare providers upon detection of a fall or impact. When an inprogress serious hip-impacting fall is detected, an airbag will deploy to physically protect the hip region from potential major injury. The Tango Belt is for prescription use only.

4. Study Design, Duration, Objectives and Endpoints

4.1 Study Design

This is a multi-center, comparative, adaptive, non-significant risk clinical trial conducted in the United States to assess the safety and efficacy of the Tango Belt within senior care settings. Effectiveness of the Tango Belt will be determined by analysis of evidence for the Tango Belt as an adjunctive intervention to the standard-of-care (SOC) to mitigate major hip injuries from falls in an older adult population at-risk for fall injury as the primary endpoint. Performance of the Tango Belt to mitigate fall injuries that result in hip fracture, emergency room visits, and hospitalizations will be secondary endpoints. The performance of the device is determined by the comparison of the proportion of fall-related major hip injuries in the intervention group as compared to the proportion of fall-related major hip injuries in a retrospective control group utilizing only SOC. SOC utilization will be verified for each clinical site enrolled. An adaptive trial design will be utilized to allow an initial efficacy target to be evaluated at 6 months; if the initial target is not met, then a second cohort of sites and subjects will be enrolled for an additional 6 months to allow a lower efficacy target to be evaluated.

Safety of the device will be determined by analysis of adverse events as an ancillary endpoint.

4.2 Duration (per site)

Estimated enrollment time 3 months
Estimated in-study run time 6 months

Estimated total duration 12 months after 1st patient enrolled

4.3 Objectives

Primary Objective: To assess the performance of the Tango Belt to mitigate fall-related major hip injuries in an at-risk of fall adult population as compared SOC only.

Secondary Objective: To assess the performance of the Tango Belt to mitigate falls resulting in: (1) hip fractures, (2) emergency department visits or (3) hospitalizations.

4.4 Endpoints

Primary Endpoint: The primary outcome measure will be the proportion of major hip injuries due to fall in the subjects receiving SOC as compared to subjects receiving SOC plus the Tango Belt.

Secondary Endpoints: Secondary outcome measures include the proportion of each of the following:

- Hip fractures due to fall in the subjects receiving SOC as compared to subjects receiving SOC plus the Tango Belt.
- Emergency Department visits due to fall in the subjects receiving SOC as compared to subjects receiving SOC plus the Tango Belt.
- Hospitalizations due to fall in the subjects receiving SOC as compared to subjects receiving SOC plus the Tango Belt.

Ancillary Endpoints: Ancillary endpoints will include:

- Adverse events
- Major injuries due to fall
- Fall occurrence
- Device wear adherence
- Device fall alerts
- Device discrimination of serious hip-impacting vs. non-serious hip and non-hip impacting falls
- Airbag deployment
- FES-I short version

5. Selection of Subjects

- **5.1 Inclusion Criteria**: All subjects are required to meet ALL of the following inclusion criteria to be considered eligible for participation in this study:
 - 1. Age 65 years or older;

- 2. Have experienced a fall-related fracture after age 50 -OR-
 - Have experienced one or more falls in the 12-months prior to consent and have a diagnosis of osteoporosis, osteopenia, or prescribed osteoporosis medication.
- Independently or with staff or caregiver assistance, able to transfer between surfaces (e.g., to or from a bed, chair, wheelchair, toilet, standing position) or walk or move between locations (use of an assistive device such as a walker is acceptable);
- 4. Have a waist circumference between 29 50 inches (63.5 127 cm);
- 5. Able to comply with required study procedures and follow-up schedule as determined by the Study Investigator;
- 6. Are under the care of the Investigational organization;
- 7. Provides consent or their legally authorized representative provides consent on subject's behalf
- **5.2 Exclusion Criteria**: Subjects will be excluded from participating in this study if they meet ANY of the following exclusion criteria:
 - 1. Age 64 years or less;
 - 2. Participation in a different clinical investigation that can conflict with this clinical study as determined by the Study Investigator and approved by the Sponsor;
 - 3. Total dependence on staff or caregiver assistance to be able to transfer between surfaces (e.g., to or from a bed, chair, wheelchair, toilet, standing position) and walk and move between locations;
 - 4. Use of other devices or interventions outside of SOC for fall risk management during study participation without Sponsor approval;
 - 5. Unable to comply with required study procedures and follow-up schedule as determined by the Study Investigator;
 - 6. Does not provide consent, or legally authorized representative does not provide consent

5.3 Strategies for Recruitment and Retention

Control group: The investigator or designee will retrospectively review the site's EMR database to determine their long-term care patient population's initial eligibility for meeting the study inclusion criteria. The subjects in the clinical site census at the time frame 6 months prior to the IRB approval date will be screened for eligibility for study inclusion. Subjects eligible for the control group must meet the requirements of the inclusion and exclusion criteria except for the waist circumference and need for consent. Eligible subjects' electronic health records will be mined for the baseline, midpoint, and

final study metrics. If there is an insufficient number of eligible subjects to meet the control group target (defined as 4 times the expected number of intervention group subjects to be enrolled from the site) at 6 months prior to the intervention group start date, the EMR database screen will extend retrospectively in 6 month increments until the control group target is reached.

Intervention group: The investigator or designee will review the site's EMR database to determine their current long-term care patient population's initial eligibility for meeting all study inclusion and exclusion criteria, except for waist circumference, informed consent, and ability to comply. Subjects meeting initial eligibility will then have their waist circumference obtained, and those that meet inclusion criteria will then be offered the opportunity to participate in the study through the informed consent process utilizing IRB approved subject facing recruitment materials including a video introduction of the device, a flyer on the device and research study and verbal explanation of the study with access to study site investigator for addressing questions and/or concerns. If the subject agrees to be a participant in the study, the subject will be given a written informed consent to read, sign and date (Appendix 1 - Informed Consent). If the subject has a Legally Authorized Representative (LAR) or Person of Authority (POA) in place, the POA will receive notification regarding the eligibility for the subject to participate in the study with the IRB approved subject facing recruitment materials including video introduction of the device, a flyer on the device and research study and verbal explanation of the study with access to study site investigator for addressing questions and/or concerns with the written informed consent. The POA may offer consent verbally over the phone to the investigator/ designee with notation on the Informed Consent Form and subsequent receival of copy of the ICF via USPS or email. The ICF can also be signed electronically with a provided eSignature option to the POA. All subjects or POAs will be given the opportunity to discuss the technology, risks, potential benefits, alternative therapies, and the study requirements with the investigator prior to signing the informed consent. Subjects or their POAs that provide written or electronic consent will be preliminarily enrolled into the intervention group.

Upon preliminary enrollment, utilization of the Tango Belt will be prescribed by the site's physician and written into the subjects' plan of care at the care residence. A Tango Belt of appropriate size based upon waist measurement will be provided to the subject by the investigator or designee. The subject will be assigned to the Tango Belt ID located in the APT cloud electronically via Tango Belt companion app for data tracking. The Tango Belt size will be adjusted for most comfortable and appropriate fit using the sizing strap located in the left side zipper pocket of the Tango Belt. The Tango Belt will be prescribed to be worn up to 24 hours/ day with removal for bathing activities, dressing as needed, twice a week at minimum for charging and upon subject request. Baseline metrics will be obtained from the subjects' EMR. The enrolled participant will be

assessed for cognition level via the BIMS if this has not already been taken as part of the EMR. Assessment of balance confidence using the short version of the FES-I if they are cognitively capable of completing the survey with a BIMS Score of 13-15. (Appendix 2 – Study Questionnaire)

Enrolled subjects in the intervention group will then proceed through a run-in period of 14 days to assess adherence to utilization of the Tango Belt. At 14 days, if the subject is demonstrating adherence to use of the device of at least 64% as viewed by the investigator or designee in the Tango Belt companion app dashboard as "Compliance" (defined as wearing the device for at least 1 hour per day for at least 9 of 14 days), they will be fully enrolled into the study and proceed through the study duration. Subjects who do not meet the run-in period requirement will be withdrawn from the study.

Screen Failures in this study would include study candidates that:

- Do not meet inclusion criteria
- Meet any exclusion criteria
- Do not fit within the range of Tango Belt sizing available
- Do not comply with the minimum device utilization of 64% within the run-in period

To account for the relatively high morbidity and mortality of the target study population, we will assume a 20% in-study attrition rate, and thus will aim to over-recruit by this amount beyond the target sample size statistically required for the intervention group.

Lastly, after 6 months of in-study participation, intervention subjects may be given the option to continue wear of the Tango Belt in order to collect longer-term safety and efficacy data. In an effort to minimize potential for bias, this option will not be revealed to intervention subjects prior to study enrollment.

5.4 Participant Withdrawal/Discontinuation or Termination

All subjects will be followed for 6 months following enrollment in the study to ensure study inclusion and exclusion criteria continue to be met; any subject who no longer meets the study criteria during this timeframe will be withdrawn. Intervention subjects will be advised that they may voluntarily withdraw from the study at any time without jeopardy to any future medical care and will be instructed to notify the investigator or designee immediately should they wish to do so. If any intervention subject wishes to withdraw from the study, the reason(s) for discontinuation will be recorded in the subject's chart and on the appropriate Case Report Form (CRF). Intervention subjects

may choose to withdraw for any reason and are not obligated to reveal their reason(s) for withdrawal.

Any screen failure, withdrawal/discontinuation or termination of a subject from the study will be accompanied by the date, the reasoning specific to the removal from study and data captured prior to removal will be recorded on the CRF.

If a significant symptom or adverse event is associated with discontinuation, this will be recorded in the CRF and patients who are withdrawn due to adverse events will be followed until resolution or stabilization of the adverse event.

If an intervention subject is demonstrating adherence to utilization of the device under 64% during the initial 14-day run-in period, they will be withdrawn from the study.

It is also recognized that the investigator, at his or her discretion, may withdraw a subject from this trial to pursue other treatment modalities, if the subject no longer meets the study inclusion and exclusion criteria, or if the subject cannot continue in the trial for any medical reason(s). The sponsor is to be notified in a timely manner if the subject is to be withdrawn and a Study Termination Form will be completed.

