7.2 Evaluations and Scheduled Data Collection Flow Chart

Evaluation	Visit 1 Screening/ Baseline Visit (+/- 14 days)	Visit 2 14-day Run-In (+/- 2 days)	Visit 3 90-Days (+/- 10 days)	End of Study 180-days (+/- 30 days)	Unscheduled Visit /
Render Informed Consent	Х				
Demographic information	Х				
Medical / Fall history	х				
BIMS	Х				
Fall mitigation plan of care	Х		Х	Х	Х
FES-I (short version)	x		Х	Х	Х
Inclusion/Exclusion criteria review	Х		Х	Х	Х
Tango Belt adherence		Х	Х	X	Х
Adverse Events (including Fall event information)			Х	Х	Х
Device deficiencies			Х	Х	Х

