6.3 METHODS FOR WITHDRAWALS AND MISSING DATA

All practical monitoring and follow-up steps will be taken to ensure complete and accurate data collection. Since endpoints are assessed at the 180-day visit, it is anticipated that there will be approximately 30% attrition. Given the disproportionately high rate of death and other loss-to-follow up reasons within this population, multiple imputation approaches will be carried out for missing primary endpoint data on the ITT population. The primary effectiveness analysis will be performed on data that has the primary outcome multiply imputed.

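### Subjects who lose eligibility after enrolment are withdrawn and their outcome collection stops, although the endpoints could still be read from the facility record to day 180

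*Combined protocol and SAP*

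**What the plan says.** Protocol 5.4 follows all subjects for six months to confirm that the entry criteria still hold, and states that "any subject who no longer meets the study criteria during this timeframe will be withdrawn". The last paragraph of the same section says that the investigator may, at discretion, withdraw a subject in exactly that situation. One sentence is mandatory and the other permissive.

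The flow chart in protocol 7.2 schedules "Inclusion/Exclusion criteria review" at day 90, day 180 and unscheduled visits as well as at baseline. Criteria in 5.1 and 5.2 that can change after entry include:

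- total dependence "on staff or caregiver assistance to be able to transfer between surfaces" and to move between locations (exclusion 3);
- "Unable to comply with required study procedures and follow-up schedule as determined by the Study Investigator" (exclusion 5);
- a waist of 29 to 50 inches (inclusion 4).

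On removal, 5.4 provides that "data captured prior to removal will be recorded on the CRF". A symptom or adverse event tied to discontinuation is also recorded, and "patients who are withdrawn due to adverse events will be followed until resolution or stabilization of the adverse event". No text continues endpoint collection to day 180 after withdrawal.

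The endpoints themselves are extracted from the site's MDS or EMR (protocol 7.3) over the period from enrolment to the 180-day visit (SAP 3.2.1). SAP 6.3 says "it is anticipated that there will be approximately 30% attrition". SAP 6.3.1 attributes missing primary endpoints mainly to premature withdrawal and imputes them from baseline covariates only. SAP 6.2.2 drops incomplete controls without imputation.

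**The concern.** Leaving the study and leaving the belt are treated as one event. A resident who loses eligibility at day 60 may still live at the site and be charted there daily, yet a hip fracture or ED visit at day 100 would not enter the trial. The outcome is missing because of a rule, not because it is unobtainable.

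The reasons for loss are unlikely to be neutral. Dependence may follow a fall, an illness or general decline. Inability to comply may follow belt discomfort. Weight loss can take a waist out of range. Each may be related to prognosis or to belt tolerance.

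The loss can also differ between groups. Controls are read retrospectively and have no study procedures to comply with, and the waist criterion is waived for them (protocol 5.3, SAP 5.1). The comparison is not randomized and expects few belt events, so a differential loss of this kind bears directly on the primary result and on whether the ITT analysis follows subjects as assigned.

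**Working it through.** **1. Reproduce the plan's attrition figures.** SAP Section 4 and its Summary give 94 evaluable belt subjects at the interim and 188 at the final analysis, with 30% attrition.

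- 94 / (1 − 0.30) = 134.3; stated 134.
- 188 / (1 − 0.30) = 268.6; stated 268.

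Both agree apart from rounding. Expected loss at the interim size is 0.30 × 134 = 40.2, about 40 subjects.

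**2. Control risk.** SAP Section 4 reports 15% as the proportion observed among controls; the SAP Summary and 4.1 call it annual. The base sizes are approximated only with 15% as a six-month risk: a continuity-corrected two-proportion formula with 1:2 allocation and a two-sided Pocock nominal level of 0.0294 gives 95 and 183, against 94 and 188. I use 15% as the six-month risk here and show the annual reading in step 5.

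**3. Assumptions the documents do not supply.** A quarter to a half of the 40 (10 to 20) are residents withdrawn under this rule whose records remain accessible. They leave at day 90. They run at belt risk before leaving and at control risk afterwards, with constant hazards.

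**4. Belt risk if they are restored.** The 180-day risk of a restored subject is 1 − √[(1 − belt risk) × (1 − 0.15)].

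| | 60% effect | 80% effect |
|---|---|---|
| Belt risk on the belt | 0.40 × 15% = 6.0% | 0.20 × 15% = 3.0% |
| Events in 94 | 5.64 | 2.82 |
| Risk of a restored subject | 1 − √(0.94 × 0.85) = 10.6% | 1 − √(0.97 × 0.85) = 9.2% |
| Restore 10 | (5.64 + 1.06)/104 = 6.4% | (2.82 + 0.92)/104 = 3.6% |
| Restore 20 | (5.64 + 2.12)/114 = 6.8% | (2.82 + 1.84)/114 = 4.1% |

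Against 15%, an apparent 60% reduction becomes about 57% to 55%, and an apparent 80% reduction about 76% to 73%.

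**5. If 15% is annual** (7.5% per six months), the same steps give:

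- 60% effect: restored risk 1 − √(0.97 × 0.925) = 5.3%; belt risk moves from 3.0% to (2.82 + 0.53)/104 = 3.2% or (2.82 + 1.06)/114 = 3.4%.
- 80% effect: restored risk 1 − √(0.985 × 0.925) = 4.5%; belt risk moves from 1.5% to (1.41 + 0.45)/104 = 1.8% or (1.41 + 0.91)/114 = 2.0%.

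**6. Does imputation remove the gap?** At 30% missing, the 20% trigger in SAP 6.3.1 is met. The model contains no withdrawal reason, wear or later mobility. Controls are not imputed, so it appears to be fitted to retained belt subjects (my inference). Baseline differences aside, it would then assign the lost subjects about the retained risk, 6.0% or 3.0%. Replacing 10 to 20 imputed outcomes among 134 by real ones gives:

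- 60% effect: (124 × 0.06 + 1.06)/134 = 6.3% to (114 × 0.06 + 2.12)/134 = 6.7%.
- 80% effect: (124 × 0.03 + 0.92)/134 = 3.5% to (114 × 0.03 + 1.84)/134 = 3.9%.

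On these assumptions the gap narrows slightly but does not close.

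**The case against.** Much of the opposing case stands.

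- **Safety.** A reader might infer that the harm which made someone stop the belt goes unrecorded. Section 5.4 says otherwise: it is recorded, and adverse-event withdrawals are followed for that event. Only new, later events are lost.
- **Low wear.** A reader might infer that poor wear after enrolment triggers withdrawal. The only wear-based withdrawal is the 14-day run-in; 5.3 lets the belt come off on request, and the adherence population (SAP 5.2.3) is what excludes subjects injured off the belt. Injuries off the belt therefore count in ITT while the subject remains enrolled. Refusal matters only through voluntary withdrawal or if the investigator judges it an inability to comply.
- **Controls.** The rule covers all subjects, so dependence nominally applies to both groups. The asymmetry is confined to compliance and waist size, and to the handling of incomplete records.
- **Direction.** A reader might infer that the rule necessarily favours the belt. A hip injury that causes dependence would normally be captured before removal. If injured subjects are kept as events and uninjured withdrawals become missing, a complete-case analysis leans against the belt.
- **Attrition.** A reader might infer that the rule drove the planning figure from 20% to 30%. SAP 6.3 cites death and other loss to follow-up, and SAP Section 9 cites only higher-than-expected loss. Neither names this rule.

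What the objection does not answer is that no text continues outcome extraction after withdrawal, and that the imputation model cannot see why a subject left.

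**Conclusion.** The concern holds in a limited form. Followed as written, the plan leaves uncollected the outcomes of withdrawn residents that may still be available at the site. The loss may be informative and may differ between groups, and the planned imputation does not correct that. Separately, the mandatory and discretionary sentences in 5.4 contradict each other, so sites could apply the rule differently.

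Neither the direction nor the size of the bias can be established, because attrition is not split by reason. The shift from 6.0% to 6.4–6.8%, or from 3.0% to 3.6–4.1%, is an illustration. It rests on an assumed share of 10 to 20 subjects, mid-study exit, control risk after stopping and 15% as a six-month risk.

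A larger figure is tempting: the 0.8 to 1.6 injuries expected after exit (10 to 20 subjects × 7.8%, where 7.8% = 1 − √0.85), divided by 5.64 or 2.82 expected belt events, gives 14–28% or 28–55%. That leaves the restored subjects out of the denominator and overstates the change in risk.

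**What to change.** In protocol 5.4:

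1. Reconcile the mandatory and discretionary withdrawal sentences.
2. Separate belt discontinued or eligibility lost (date and reason recorded) from withdrawal of authorization for data, which 13.4 already treats as its own event.
3. For every subject past run-in who has not withdrawn authorization and whose records remain accessible, continue the same 90- and 180-day extraction of falls, major hip injuries, hip fractures, ED visits, hospitalisations, deaths and adverse events.
4. Analyse these subjects in the ITT population, and state the same rule for controls.

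Clinical decisions about belt use and medical withdrawal stay with the investigator, unchanged. Residents who transfer out may not be reachable through the site's record and would remain missing. For subjects already exited, the extraction might be done retrospectively if consent and IRB terms allow.

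The cost is an amendment to the wording and a few more records to extract. The belt effect may look smaller, because injuries off the belt will count.
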